### **Metals labs**

The handling of the trace metals analyses and biorepository will be available in the MOP for each of these study units. If the lead or cadmium levels measured by the Trace Metals Laboratory are outside the upper boundaries for American Conference of Governmental Industrial Hygienists (ACGIH) (after a repeated measurement at the Trace Metals Laboratory) the clinical site and the CCC will be notified. In most cases, this will require repeating the levels in a commercial lab. If levels are still high, the participant will be recommended to contact their local public health department who will follow standard procedures for the evaluation of metal exposures. Because removal from exposure is the primary treatment, this should not interrupt the TACT2 infusions. The study sample is unlikely to have any such values.

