The above metal collections and biorepository will serve to support analyses to determine whether post-infusion urine metal measurements, alone and in comparison to the corresponding pre-infusion measurements, have clinical significance for predicting outcomes and clinical benefit of chelation; and whether the suite of additional metal levels measured in blood and urine by inductively coupled plasma mass multi-element analytic technique, some of which are not chelated by edetate disodium, have clinical (prognostic) significance in preliminary testing

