### Preliminary data on metal excretion following a TACT2 infusion

A preliminary study measured metal excretion after one infusion of placebo, and one of active chelation. Twenty male participants (mean age 66, range 51 to 81) were recruited using the same criteria as in TACT (post-MI, age  $\geq 50$ , creatinine  $\leq 2.0$  mg/dL). Urinary concentrations of 20 toxic metals (Al, Sb, As, Ba, Be, Bi, Cd, Cs, Gd, Hg, Pb, Ni, Pd, Pt, Te, Tl, Th, Sn, W, U) normalized to creatinine excretion were measured at baseline, for 6 hours following a placebo infusion of 500 mL normal saline and 1.2% dextrose, and for 6 hours following a 3 gram edetate disodium-based infusion as used in TACT.

Following an edetate disodium-based TACT infusion, there was a striking increase in the urinary excretion of lead (mean 3,926% increase,  $P < 0.001$ ; Figure A), cadmium (739% increase,  $P < 0.001$ ; Figure B), and nickel (131% increase,  $P < 0.001$ ). There was also a modest increase in the urinary excretion of tin and thallium (30-40%;  $P < 0.05$ ). These preliminary data show that

Effect of Placebo or Edetate disodium-based infusion on urinary lead (A) and cadmium (B) excretion\*

\*Lines represent individual patient data points. Bar graphs are mean  $\pm$  SD of % change from baseline.

an edetate disodium-based infusion, identical to that used in TACT and proposed for TACT2, markedly increased excretion of lead and cadmium. Whether enhanced excretion of metals following repeated chelation infusions leads to a reduction in blood lead or pre-infusion urine cadmium (reflecting total body stores of each) is unknown, but will be identified by TACT2.

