## 6. STUDY PROCEDURES

### 6.1 Schedule of Evaluations

SCHEDULE OF EVALUATIONS									DCRI Call Center Data Collection
		Clinic Visits							Infusion Phase
	Screening	Every Inf	Inf 1	Inf 5	Inf 10	Inf 20	Inf 30	Inf 40	Months 6, 12, 16, 20, 24, 28, 32, 36, 40, 44, 48, 52, 56, 60
Assess Inclusion / Exclusion Criteria	X								Every Call
Obtain Informed Consent and Medical Records Release Form	X								
Contact Information	X								
Demographics	X								
Medical History	X								
Complications of Diabetes	X					X		X	X
Laboratory Tests									
Creatinine	X			X	X	X	X	X	
Calcium	X			X	X	X	X	X	
Albumin	X			X	X	X	X	X	
Glucose	X					X		X	
HbA1c	X					X		X	
Microalbumin	X					X		X	
CBC/plt	X					X			
Liver Function	X								
Lipids	X							X	
Blood metals (pre/post infusions)									
Cadmium (urine)			X	X		X		X	
Lead (blood)			X	X		X		X	
Vital Signs									
Blood pressure	X	X							
Heart Rate	X	X							
Pulmonary check	X	X							
Height	X								
Weight	X	X							
Medications									
Concomitant medications	X			X		X		X	X
Study Vitamins				X	X	X	X	X	X
Endpoints									
Hospitalization		X							X
All-cause Mortality		X							X
Safety**		X							
Economic Aims									
EQ-5D	X			X		X		X	X
Resource Utilization		X							X

\* EOS = end of study

\*\*Safety assessment = every visit and 30 days post final infusion

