### **6.1.2 Laboratory Procedures**

The TACT2 laboratory procedures include safety monitoring, diabetes monitoring labs, and additional labs (metals and biorepository). Abnormalities in the safety lab results collected will be compiled and reported to the DSMB. Biosample processing, analysis, storage, and data management details are covered in the separate MOP for each laboratory.

In brief, there are 2 types of blood and urine specimens that will be sent for analysis:

1. Safety labs will be sent to study central laboratory.
2. Blood and urine for metals analyses and for preparation and storage will be sent to the TACT2 Biorepository. The Biorepository will be responsible for processing and storage of samples during the study and intermittent batch transfer of urine and blood samples to the analysis laboratory.

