For futility monitoring, TACT2 will employ a modification of the inefficacy monitoring guideline of Freidlin, Korn, and Gray to stop the trial if the chelation strategy is not beneficial. We plan to use a conservative boundary, denoted as LIB0, along with a harm look at 25% of expected information. This approach will include 4 interim looks scheduled at roughly 25%, 40%, 60%, and 80% of expected information. With the proposed design, a total of roughly 280 primary endpoint events are expected and the first interim review for futility and efficacy will be scheduled after approximately 70 primary endpoint events have been observed. The harm look at 25% of expected information would suggest stopping the trial if the data suggests harm for the chelation strategy vs. the placebo chelation with p-values <0.05 for both the primary outcome and the all-cause mortality endpoint. For the interim reviews at 40%, 60%, and 80%, the inefficacy guideline suggests stopping the trial if the chelation infusion strategy has a hazard ratio > 1.0 compared to placebo for both the primary outcome and the all-cause mortality endpoint. This inefficacy monitoring approach will result in a trivial loss of power and requires no sample size adjustment.

The method of Haybittle and Peto will be proposed as the primary guide for interpreting interim efficacy analyses. The timing of the interim efficacy analyses will correspond to the futility monitoring reviews (i.e. at roughly 25%, 40%, 60%, and 80% of expected information). The proposed efficacy monitoring guideline requires large critical

values ( $Z=3$ ,  $p\leq 0.001$ ) for every assessment until the planned final analysis. The TACT2 investigators suggest that both the primary outcome and the all-cause mortality outcome are evaluated at the interim reviews with a focus on the comparison of active chelation vs. placebo.

The CCC PI, DCC PIs, CCC staff, clinical study Co-PIs, site investigators, NIH Program Staff and study participants will remain blinded until database lock. Limited staff will be unblinded to handle randomization codes, deliver the interventions to sites, and prepare DSMB reports. The statistical staff responsible for preparing DSMB reports will not directly interact with the clinical team that delivers care to the study participants or the CEC that determines clinical events.

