### **Exploratory Endpoints**

The comparison of costs will test mean direct medical costs incurred during the study (index infusion through end of follow-up). To account for staggered entry and incomplete follow-up, costs will be adjusted using the approach of Bang and Tsiatis. Statistical comparisons will be made using a normal approximation with standard errors

estimated using the bootstrap approach. The probability of differences in cost greater than thresholds of policy interest (such as \$1000, \$2000, or \$5000) will be calculated. Differences in cost by treatment group will be interpreted in the context of the trial clinical results, looking for both consistency and plausibility. Follow-up costs will be presented both overall and by category (e.g., inpatient readmission, outpatient procedures, concomitant medications, non-acute institutional care). Cumulative costs over the study period between treatment groups will be compared. Descriptive comparisons of cost according to clinical variables defining subgroups of interest will also be performed.

The analyses for toxic metals in blood and urine in the TACT2 population will proceed in three phases. First, we will evaluate if the chelation regimen has the effect on metal internal dose that we have postulated. To do this, we will compare body metal levels (lead in blood, pre-chelation urine lead and cadmium, and post-chelation urine lead and cadmium, in separate analyses) between active and placebo chelation groups at baseline and over the treatment phase of TACT2. Second, we will relate those levels to changes in the primary clinical endpoint (a composite of death from any cause, recurrent MI, stroke, coronary revascularization, or hospitalization for unstable angina) caused by chelation therapy relative to placebo. Finally, we will perform the exploratory analyses described below.

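### The high-metal alert is not limited to pre-infusion samples, so an alert on post-infusion urine could reveal active chelation to people who must stay blinded

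*Protocol*

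**What the plan says.** **The trigger.** Protocol 7.2 (Metals labs) opens the rule with "If the lead or cadmium levels measured by the Trace Metals Laboratory are outside the upper boundaries". It names neither the specimen (blood or urine) nor the timing (before or after an infusion).

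**The recipients.** The rule continues: "after a repeated measurement at the Trace Metals Laboratory) the clinical site and the CCC will be notified". In most cases the level is then repeated in a commercial laboratory. If it is still high, the participant is advised to contact public health. The section adds that an alert should not interrupt infusions and that such values are not expected in this population. It leaves handling of the metals analyses to the MOP.

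**What is measured.** The Schedule of Evaluations (6.1) has the row heading "Blood metals (pre/post infusions" and lists urine cadmium and blood lead at infusions 1, 5, 20 and 40. Section 1.2 plans to study "whether post-infusion urine metal measurements, alone and in comparison to the corresponding pre-infusion measurements". Section 9.6 (Exploratory Endpoints) plans to compare blood lead and also "pre-chelation urine lead and cadmium, and post-chelation urine lead and cadmium" between the chelation arms, and uses post-chelation urine values at infusion 1 to define subgroups.

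**The drug effect.** Section 2.2 reports, after one active infusion, "a striking increase in the urinary excretion of lead (mean 3,926% increase", and a 739% increase for cadmium.

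**The blind.** Section 9.4 states: "The CCC PI, DCC PIs, CCC staff, clinical study Co-PIs, site investigators, NIH Program Staff and study participants will remain blinded until database lock".

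**The concern.** The alert is written for environmental exposure, but a post-infusion urine sample mainly reflects what the infusion has just mobilised. If such a sample exceeds the boundary, the likeliest explanation is active chelation. Re-measuring at the laboratory confirms the number and does not remove the drug effect. The notice goes to the site and the CCC, and may lead to advice to the participant.

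The leak would run in one direction, because only active infusions produce the rise. Two components of the primary composite, coronary revascularization and hospitalization for unstable angina, depend partly on decisions by patients and physicians. Knowledge of the arm could influence whether these events occur or are reported.

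The formal unmasking procedure in section 6.2.4 is much stricter: the CCC PI stays blind even when a treating physician is told the assignment, and the request is recorded in the eCRF. The metals alert has no such protection. SAP 2.4 reports the number of participants unmasked, but nothing says that these alerts would be counted.

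**Working it through.** **1. Fold changes (Protocol 2.2).** Fold change = 1 + percent increase / 100.
- Urine lead: 1 + 3,926/100 = 40.26.
- Urine cadmium: 1 + 739/100 = 8.39.

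These are mean increases in 20 men, over 6 hours after one 3 g infusion, normalised to creatinine. The percentages cannot be re-derived, since individual data are not given.

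**2. Which fold change applies.** The schedule in 6.1 lists cadmium in urine and lead in blood, so the scheduled urine test corresponds to the 8.4-fold figure. The 40.3-fold figure is for urine lead, which is absent from that table but is in the planned analyses of 9.6.

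**3. Timing.** Section 6.1.2 describes "intermittent batch transfer of urine and blood samples to the analysis laboratory" during the study, with no interval given. The remark in 7.2 that an alert should not interrupt infusions shows that alerts are foreseen during treatment. Follow-up for events continues after the infusions end (Protocol section 3, SAP 1.1).

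**4. Illustration of what an alert would tell the recipient.** None of the following inputs is in the documents; all are assumptions:
- the unprovoked urine level is log-normal with geometric SD (GSD) 1.5 to 2.5;
- the ACGIH limit is k = 5 to 80 times the median;
- the active post-infusion level is the unprovoked level times f, with f = 8.39 or 40.26 for everyone;
- placebo infusion causes no change (f = 1).

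Allocation to active or placebo chelation is 1:1, as in the protocol.

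P(alert) = 1 − Φ[ln(k/f) / ln(GSD)], and P(active given alert) = P(alert, active) / [P(alert, active) + P(alert, placebo)].

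Example with GSD 2.0 and k = 10:
- Cadmium, active: ln(10/8.39)/ln 2 = 0.253, so P = 40.0%.
- Placebo: ln(10)/ln 2 = 3.32, so P = 0.045%.
- P(active given a cadmium alert) = 0.400/(0.400 + 0.00045) = 99.9%.

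| GSD | k | Placebo | Cadmium, active | Lead, active | P(active given alert), cadmium / lead |
|---|---|---|---|---|---|
| 1.5 | 5 | 0.004% | 89.9% | 100% | 100% / 100% |
| 1.5 | 80 | 0.0% | 0.0% | 4.5% | 100% / 100% |
| 2.0 | 10 | 0.045% | 40.0% | 97.8% | 99.9% / 100% |
| 2.0 | 40 | 0.0% | 1.2% | 50.4% | 100% / 100% |
| 2.5 | 5 | 4.0% | 71.4% | 98.9% | 94.8% / 96.2% |
| 2.5 | 80 | 0.0% | 0.7% | 22.7% | 100% / 100% |

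Values are rounded, and 100% means nearly 100%. Across the full grid, the chance of an alert per active post-infusion sample runs from about 0% to 90% for cadmium and from 4.5% to 100% for lead. On placebo it is at most 4.0%. The frequency of alerts is thus undetermined, but what an alert would convey is fairly stable: about 95% to nearly 100% probability of active chelation.

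**5. With pre-infusion samples only.** The acute rise no longer enters the trigger. In the same illustration the alert probability is the unprovoked one, 0% to 4.0%, with no acute difference between arms.

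**The case against.** **Pre-infusion samples may have been meant.** Section 1.2 defines internal dose by blood lead and urine cadmium, and 2.2 treats blood lead and pre-infusion urine cadmium as the measures of body stores. The rule in 7.2 speaks of exposure, public health and values that are not expected, all of which fits unprovoked levels. This is a fair reading of the intent, but the rule does not say so. The expectation that high values are unlikely does not address samples for which the protocol itself reports 8- to 40-fold mean rises.

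**The MOP may restrict the samples.** This stands. It cannot be checked, and if it is so, one clause in 7.2 settles the point.

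**The repeat test and adjudication limit the harm.** Referral follows only a second high result. Section 2.2 says over 95% of EDTA is excreted within 24 hours, so a repeat drawn well away from an infusion would largely avoid the effect. But the site and the CCC have already been notified by then, and the timing of the repeat is not stated. The CEC adjudicates every primary component except revascularization, which it clinically confirms (10.3.3). That protects classification, but not whether an event occurs or is reported.

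**Stronger readings that a reader might infer.**
- *The alert would reveal the arm.* An alert needs a value above a boundary that is not in the documents, applied to absolute levels that are not given either.
- *Anyone on active infusion with a pre-infusion value above 2.5% (1/40.26, lead) or 12% (1/8.39, cadmium) of the limit would trigger one.* This applies a group mean to each individual. The pilot used one 3 g infusion, whereas section 5.1 adjusts the dose up to that maximum, and no post-infusion collection window is stated.
- *A count of patients can be given.* Taking 2% to 20% of about 500 active patients gives 10 to 100, but no document supports those shares.

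**Conclusion.** The concern holds as a gap in the written rule. Followed literally, 7.2 sends alerts on post-infusion samples to people whom 9.4 keeps blind, and such an alert could reveal active chelation. The supporting facts are in the protocol: an unrestricted trigger, measured post-infusion urine, and reported mean rises of 8.4-fold for cadmium and 40.3-fold for lead. That an alert would be highly informative rests on the assumptions in the illustration, chiefly that placebo infusion leaves urine levels unchanged.

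The number of participants affected cannot be determined and may be zero. It depends on the ACGIH boundaries, the absolute urine levels, the timing of the batches and the content of the MOP. The documents do not show that anyone was unblinded. Because the possible bias concerns the primary composite and the remedy is nearly free, the change should be made.

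**What to change.** In Protocol 7.2 (Metals labs), with matching text in the laboratory MOP, state that:

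1. the ACGIH check and the notification apply only to samples drawn before an infusion, which the laboratory identifies from the sample label;
2. post-infusion metal values are not released to the site, the CCC or the participant before database lock;
3. any commercial-laboratory repeat is drawn before an infusion.

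The labels described in 6.2.2 already carry patient number, infusion number and sample type, so the laboratory should be able to sort the samples itself. The alert need not be routed through unblinded coordinating-centre staff. Doing so would also sit badly with 9.4, which keeps the statisticians who prepare DSMB reports apart from the clinical team.

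The cost is one paragraph. The small downside is that a high value seen only in a post-infusion sample would not be notified before database lock.

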### **Clinical Assessments**

In TACT, the principal concern that emerged related to the weekly infusions of 500 ml of fluid and the potential precipitation of heart failure (HF). Patients are not eligible for TACT2 if they have had a hospitalization for heart failure in the 6 months preceding initial eligibility assessment. Nonetheless, like in TACT, in order to reduce ongoing patient risk, weight will be monitored at each infusion. If there is weight gain of 3 lbs or more since the last infusion, or 5 lbs or more since the screening evaluation, the patient will be evaluated for heart failure. A trained study coordinator or infusion nurse may perform this examination. If there is HF present, this will be entered into the EDC, the infusion delayed for 1 week, and a suitable treatment regimen developed with the patient's clinical physician.

## **7.3 Adverse Events and Serious Adverse Events**

### **Adverse Event (AE)**

An adverse event is any undesired, noxious or pathological change in a patient as indicated by signs, symptoms, or laboratory changes that occur in association with the use of trial intervention/medication, whether or not considered drug or biologic related. This definition includes intercurrent illness or injuries, exacerbation of existing conditions, psychological events, psychosocial events, associated temporally associated with the use of a pharmaceutical product or study intervention. Pre-existing conditions, which worsen during a study, are considered adverse events and can become serious if they fulfil one of the seriousness criteria described below.

Note: Diseases, signs, symptoms, and/or laboratory abnormalities already existing at study admission are not considered adverse events when observed during the trial unless they represent an exacerbation in intensity or frequency. (Definition modified from ICH-E2B)

### **Assessment of Adverse Event Intensity**

The intensity of an adverse event is an estimate of the relative severity of the experience made by the investigator based on his or her total clinical experience and familiarity with the literature. The maximal intensity reported during the evaluation period should be recorded. The intensity of adverse events will be characterized as mild, moderate or severe as follows:

Mild	Events are usually transient, require no special treatment, and do not interfere with the patient's daily activities.
Moderate	Events usually introduce a low level of inconvenience or concern to the patient and may interfere with daily activities, but are usually ameliorated by simple therapeutic measures.
Severe	Events interrupt a patient's usual daily activity and generally require systemic drug therapy or other treatment.

### **Assessment of Causal Relationship**

A medically-qualified investigator must assess the relationship of any AE to the use of study drug, based on available information, using the following guidelines:

1. Related – There is a reasonable possibility that the adverse event may have been caused by the study intervention
2. Not Related – There is not a reasonable possibility that the adverse event may have been caused by the study intervention

Adverse event collection and recording procedures must be designed to meet DSMB review and regulatory submission requirements, and ensure drug safety.

### **Expectedness**

The expectedness of an adverse event or suspected adverse reaction shall be determined according to the most current investigator's brochure or product label. "Expected" is defined as an adverse drug experience, the specificity and severity of which is consistent with the current investigator brochure or the risk information in the investigational plan. This term relates only to the drug, not the patient's underlying condition. Any AE that is not identified in nature, severity, or specificity in the current study drug reference document(s) (e.g., investigator's brochure) is considered unexpected. Events that are mentioned in the investigator's brochure as occurring with a class of drugs or as anticipated from the pharmacological properties of the drug, but not specifically mentioned as occurring with the particular drug under investigation are considered unexpected. For example: Hepatic necrosis would be unexpected if the

investigational brochure or plan only referred to elevated hepatic enzymes or hepatitis.  
(Adapted from 21 CFR Part 312. 32)

### **Serious Adverse Event (SAE)**

An adverse event or suspected adverse reaction is considered serious if it results in any of the following outcomes:

1. Death
2. Life-threatening
3. Persistent or significant disability/incapacity,
4. Requires or prolongs hospitalization
5. Congenital anomaly/birth defect
6. Important medical events that may not result in death, be life-threatening, or require hospitalization may be considered serious adverse events when, based upon appropriate medical judgment, they may jeopardize the patient and may require medical or surgical intervention to prevent one of the outcomes listed in this definition. (Source CFR: 21 CFR 312.32)

